4.1.1 Discharge Criteria

All urine and fecal collections will be analysed for radioactivity levels to determine if a discharge criterion is met. Participants will be confined to the study site until at least Day 8. Participants will be discharged from the study site on Day 8 if one of the following discharge criteria is met:

 \geq 90% of the total dose of radioactivity administered has been recovered in urine and feces;

OR

There is $\leq 1\%$ of the total administered radioactivity in each of 2 consecutive 24-hour intervals where both a urine and fecal sample is provided.

If neither discharge criterion is met by Day 8, participants will remain confined until at least one discharge criterion is met or up to a maximum stay of 21 days post-dose (ie, Day 22).

4.2 Scientific Rationale for Study Design

This clinical study will characterise the absorption, metabolism, excretion and mass balance of of IDV184001 in healthy adult male participants.

A comparator is not necessary for the evaluation of the objectives. Blinding of the study treatment is not required as there is no comparator. Conducting the study in healthy participants mitigates the potential confounding effects of the disease state and concomitant medications.

The study design is consistent with the FDA May 2022 guidance for industry: "Clinical Pharmacology Considerations for Human Radiolabelled Mass Balance Studies" (FDA 2022). The aim of the present study is to characterise the plasma exposure, clearance pathways, and excretion routes of IDV184001 in healthy participants after oral administration, by collecting blood (for whole blood and plasma), urine, and fecal samples for TRA analysis, plasma samples for drug concentration analysis, and plasma, urine, and fecal samples for metabolic profiling. The study will provide data required to evaluate the mass balance and the metabolic profile of [¹⁴C]-IDV184001 in humans.

4.3 Justification for Dose

INDV-2000: The single dose of 200 mg IDV184001AN (INDV-2000) selected for this study is within anticipated therapeutic range.

The planned radioactive dose of approximately 100 μ Ci of [¹⁴C]-IDV184001AN is expected to provide a sufficient radioactive signal to achieve the study objectives with minimal radiation risk to participants.

4.4 End of Study Definition

The end of the study is defined as the discharge or early termination date.

A participant is considered to have completed the study if the participant completed dosing, did not discontinue or terminate the study early, and has completed the discharge criteria (Section 4.1.1).

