- 4. To be conducted prior to the discharge from study unit. Participant will be discharged from the study unit as of Day 8, after at least one discharge criterion is met or after the maximum stay of 21 days post-dose, on Day 22. Since an approximate 24-hour time lag is anticipated for TRA measurement, actual participant release from the study site may occur 1 day after a discharge criterion is met.
- 5. Participant who terminate the study early will be asked to return to the study site 7±2 days after dosing for follow-up procedures, and to determine if any AE has occurred since the last study visit.
- 6. For details on Check-In Criteria, see Section 8.1.5.
- 7. Height collected at screening only.

INDV-2000 Clinical Study Protocol: INDV-2000-105 Final

Indivior 15 May 2023

- 8. Samples for serum chemistry will be obtained after a fast of at least 12 hours, however, in case of dropouts or rechecks, participants may not have fasted for 12 hours prior to when the serum chemistry sample is taken.
- 9. To be collected within 2 hours prior to dosing (pre-dose) and at 1 hour (±20 minutes), 2 hours (±20 minutes), and 4 hours (±20 minutes) post-dose.
- 10. To be collected within 2 hours prior to dosing (pre-dose) and at 1 hour (±15 minutes), 2 hours (±15 minutes), and 4 hours (±15 minutes) post-dose.
- 12. For blood sample collection time points, please refer to Section 10.4 (Appendix 4).
- 13. Blood samples will be samples will be collected for at least 168 hours post-dose, at the time points indicated. If neither discharge criteria (see Section 4.1.1) is met by 168 hours post-dose (ie, Day 8), sampling for TRA determination (plasma and whole blood) and metabolite identification, profiling and quantitation (plasma) will continue every 72 hours thereafter, until at least one discharge criterion is met or up to a maximum stay of 21 days post-dose (ie, Day 22).
- 14. Urine collection for analysis of TRA and metabolite identification, profiling and quantitation will be conducted at the following intervals: pre-dose (spot collection), 0 to 4, 4 to 8, 8 to 12, and 12 to 24 hours post-dose, and in 24-hour intervals until at least 168 hours post-dose (ie, Day 8). If neither discharge criteria (see Section 4.1.1) is met by 168 hours post dose (ie, Day 8), urine collection will continue in 24-hour intervals thereafter, until at least one discharge criterion is met or up to a maximum stay of 21 days post-dose (ie, Day 22).

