- 15. Positive test result for alcohol and/or drugs of abuse at the Screening Visit or at check-in.
- 16. Concurrent treatment or treatment with an investigational drug or device within 30 days or 5 half-lives (whichever is longer) prior to dosing of study drug.
- 17. Blood donation of approximately 500 mL or more within 56 days or plasma donation within 7 days prior to the Screening Visit.
- 18. Known hypersensitivity to INDV-2000.
- 19. Has less than 1 bowel movement every 2 days.
- 20. Recent history of abnormal bowel movements, such as diarrhea, loose stools or constipation, within 2 weeks prior to dosing of study drug.
- 21. Has received radiolabelled substances or has been exposed to radiation sources over the past 12 months or is likely to receive radiation exposure or radioisotopes within the next 12 months such that participation in this study would increase their total exposure beyond the recommended levels considered safe (ie, weighted annual limit recommended by the FDA 21CFR361 of 3000 mrem; FDA 2023).
- 22. Site staff and/or participants who have a financial interest in, or an immediate family member of either the site staff and/or Indivior employees, directly involved in the study.

- 23. Major surgical procedure (as defined by the Investigator) within 90 days prior to dosing of study drug or still recovering from prior surgery.
- 24. Concurrent enrolment in another clinical study, unless it is an observational study.
- 25. Participants who are unable, in the opinion of the Investigator, to comply fully with the study requirements.
- 26. Any condition that, in the opinion of the Investigator or Indivior, would interfere with evaluation of the study drug or interpretation of participant safety or study results.

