5.6 Early Discontinuation

A participant will be considered an early discontinuer if the participant received study drug and did not complete all visits or did not complete discharge criteria. Reasons for not completing all visits will be captured in the participant source documents and CRF.

The definition of a study completer is provided in Section 4.4.

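### A participant who stays to the planned Day 22 maximum without meeting a discharge criterion is labelled an early discontinuer, which could understate the completer count

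*Protocol*

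**What the plan says.** Protocol 4.4 opens by separating two ways of leaving: "The end of the study is defined as the discharge or early termination date". It then sets three conditions for a completer: he was dosed, he "did not discontinue or terminate the study early, and has completed the discharge criteria", with the criteria given by reference to Section 4.1.1.

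Protocol 5.6 makes an early discontinuer of any dosed participant who "did not complete all visits or did not complete discharge criteria", and adds: "The definition of a study completer is provided in Section 4.4".

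Protocol 4.1.1 names two discharge criteria. The first is recovery of at least 90% of the administered radioactivity in urine and feces. The second is no more than 1% "of the total administered radioactivity in each of 2 consecutive 24-hour intervals where both a urine and fecal sample is provided". For anyone who has passed neither threshold when Day 8 comes, the section says that "participants will remain confined until at least one discharge criterion is met or up to a maximum stay of 21 days post-dose". Footnote 4 of the Schedule of Events (Protocol 1.3) says the same: discharge comes "after at least one discharge criterion is met or after the maximum stay of 21 days post-dose, on Day 22".

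SAP 5.1.5 gives three routes to subject-level end of study: leaving early, meeting the discharge criteria, or finishing the 21-day post-dose stay. SAP 5.2 tabulates how many subjects completed the study, as a percentage of those enrolled, and tabulates reasons for discontinuation. The visible SAP text does not define a completer. The content of SAP 6.2, which lists changes from the protocol, is not visible.

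**The concern.** Meeting a discharge criterion is a necessary condition for completion in 4.4, and failing to meet one is sufficient for the early-discontinuer label in 5.6. The planned maximum stay appears in neither section. Everywhere else the stay is joined to the criteria by an or, so it is an alternative to them and not one of them. A participant who follows the protocol to its planned end and leaves on Day 22 with neither criterion met is therefore labelled an early discontinuer, although nothing ended early.

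At stake are the completer count in the disposition table, which will be read against the planned 6 completers (Protocol 4.1, SAP 3), and the table of discontinuation reasons, where such a participant would have no true reason to report.

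**Working it through.** **1. The plan's own figure.** Protocol 9.5 requires at least 6 participants and allows for at most 1 dropout: 6 + 1 = 7 dosed. This reproduces. The margin is 7 − 6 = 1.

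**2. Classifying the case.** Take a participant who was dosed, gave his collections to Day 22 and met neither criterion.

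| Text | What it decides | Result |
|---|---|---|
| Protocol 4.4 | Completer | No |
| Protocol 5.6 | Early discontinuer | Yes |
| Protocol 4.1.1; Schedule of Events footnote 4 | When he leaves the unit | Planned discharge at the maximum stay |
| SAP 5.1.5 | Subject-level end of study | Own route, not early termination |
| SAP Table 3 | PK Analysis Set | Label not used |

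The early-termination visit is due 7±2 days after dosing, that is 5 to 9 days post-dose (Days 6 to 10). Day 22 is 21 days post-dose, 21 − 9 = 12 days after that window closes. The visit attached to early termination cannot apply to him.

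**3. Effect on the count.** With 7 dosed, w true withdrawals and k Day 22 cases, reported completers are (7 − w − k)/7. If the stay counts as completion, the figure is (7 − w)/7.

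| w | k | As written | Stay counted |
|---|---|---|---|
| 0 | 1 | 6/7 = 85.7% | 7/7 = 100% |
| 0 | 2 | 5/7 = 71.4% | 7/7 = 100% |
| 1 | 0 | 6/7 = 85.7% | 6/7 = 85.7% |
| 1 | 1 | 5/7 = 71.4% | 6/7 = 85.7% |
| 1 | 2 | 4/7 = 57.1% | 6/7 = 85.7% |

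Each case lowers the reported rate by 1/7, or 14.3 points. One dropout and one case together take the count below 6.

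**4. When the case can arise.** The visible documents give no half-life or expected recovery, so this step rests on assumptions: first-order excretion with half-life T days, and a fraction F of 0.70 to 1.00 ultimately recoverable.

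Daily urine and feces:
- Criterion 1 is unmet at 21 days if F(1 − 2^(−21/T)) < 0.90.
- Excretion falls over time, so the last two intervals are the easiest to pass. Criterion 2 is unmet if the earlier of them, day 19 to 20, exceeds 1%: F × 2^(−19/T) × (1 − 2^(−1/T)) > 0.01.

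At F = 1.00, criterion 1 sets the lower limit: T = 21/log2(10) = 21/3.322 = 6.3 days. At F = 0.95, criterion 2 sets it: at T = 5.4, 0.95 × 0.0873 × 0.1205 = 0.010. At F = 1.00 the upper limit is T = 54.0: 0.7836 × 0.01275 = 0.010.

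| F | Half-lives with both criteria unmet at Day 22 (days) |
|---|---|
| 1.00 | 6.3 to 54.0 |
| 0.95 | 5.4 to 50.3 |
| 0.90 | 5.6 to 46.7 |
| 0.80 | 6.2 to 39.3 |
| 0.70 | 7.0 to 31.7 |

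Infrequent stools: exclusion 19 reads "Has less than 1 bowel movement every 2 days", so one movement every 2 days is eligible. Suppose feces come in every second interval and criterion 2 is read as needing two adjacent intervals. Criterion 2 then cannot be met. The case arises at any half-life if F is below 0.90, and above about 4.8 to 6.4 days if F is 0.95 to 1.00.

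Strict alternation is the extreme. With an assumed independent 50% chance of feces per interval, the chance of no adjacent pair in the 14 intervals from 168 hours to Day 22 is 987/2^14 = 987/16,384 = 6.0%. At a 70% chance it is 0.2%. If intervals without feces are skipped when reading criterion 2, a low-recovery plateau does meet it.

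**The case against.** Several points can be made for leaving the text alone.

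- *Section 4.4 cites the whole of 4.1.1, whose last sentence is the Day 22 maximum.* This lenient reading is available but weak. Section 4.1.1 uses the word criterion only for the two radioactivity thresholds, and footnote 4 and SAP 5.1.5 list the stay separately from them.
- *The texts define different things.* Sections 4.1.1 and footnote 4 govern leaving the unit, and SAP 5.1.5 defines end of study and includes early termination, so reaching end of study does not make a man a completer. This stands. The inconsistency is narrower: a planned exit that is not early termination carries the early-discontinuer label.
- *Requiring a recovery criterion is a defensible idea of completion in a mass balance study.* This stands in part. A reader might call the Day 22 participant fully observed, but the documents do not support that: his collections may be complete while excretion has not been shown to be. It is a reason to report him as a separate route, not to report him as having left early.
- *The case may be rare.* This also stands. Exclusion 20 removes men with recent constipation, and Protocol 6.9 allows milk of magnesia or prune juice from 24 hours after dosing; both make the infrequent-stool case less likely. SAP 6.4.1.2 calculates AUC to infinity only if extrapolation is at most 20%. With unlabelled sampling ending at 7 days, a mono-exponential approximation puts the half-life at 7/log2(5) = 3.0 days or less. That concerns parent and M12, not total radioactivity, so it is only suggestive.
- *The matter may be settled in text not seen.* SAP 6.2 and the separate table specifications mentioned in SAP 5.1.3 could define a completer. This cannot be excluded.

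**Conclusion.** The inconsistency is real and minor. As worded, Protocol 4.4 and 5.6 label a participant who reaches the planned maximum stay with neither criterion met an early discontinuer. Protocol 4.1.1, footnote 4 and SAP 5.1.5 treat the same exit as planned. If one such case occurs alongside one true dropout, and the protocol definition is applied, the disposition table shows 5/7 instead of 6/7 and the planned 6 completers appear to be missed.

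A reader might infer three stronger things that the documents do not support:

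- *That completion rests on the discharge criteria alone.* Section 4.4 also requires dosing and no early termination, and 5.6 also turns on completing all visits.
- *That the table will be wrong.* The miscount needs at least one case, and the frequency is unknown. It takes slow excretion (half-life about 5.4 days or more with daily feces, under the assumptions above) or low recovery with infrequent stools.
- *That the primary results are affected, because SAP 1.1 lists study discontinuation as an intercurrent event.* SAP 1.1 ties exclusion for discontinuation to having too little data, and SAP Table 3 admits participants on dosing, samples and deviations. The label enters neither, so the analysis sets and the primary PK and mass balance summaries do not change.

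**What to change.** Reconcile Protocol 4.4 and 5.6 with Protocol 4.1.1, footnote 4 of the Schedule of Events and SAP 5.1.5, for disposition reporting only. State in SAP 5.2 that a dosed participant who remained until a discharge criterion was met, or until the existing maximum stay was reached, is a completer, and that the early-discontinuer label is limited to those who left before either. Preferably tabulate completers by route, so that those who met no criterion stay visible. Add an entry in SAP 6.2, unless the definition already stands there or in the table specifications.

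The discharge criteria and the maximum stay are unchanged. The cost is one SAP sentence and one SAP 6.2 entry, best made before database lock. The wording of Protocol 4.4 and 5.6 can be aligned if an amendment is made, with the ethics review that Protocol 10.1.1 requires. There is no operational change.

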4.5 Protocol Deviations

A protocol deviation is any non-compliance with the clinical study protocol or ICH/GCP requirements. The non-compliance may be either on the part of the participant, the Investigator, or the study-site staff. It is the responsibility of the Investigator and study-site staff to use continuous vigilance to identify and report deviations to Indivior or specified designee, and to the IRB/IEC per local requirements.

5 STUDY POPULATION

Prospective approval of protocol deviations to recruitment and enrolment criteria, also known as protocol waivers or exemptions, is not permitted.

5.1 Inclusion Criteria

Participants are eligible to be included in the study only if all of the following criteria apply:

- 1. Participant must be 19 to 55 years of age inclusive, at the time of signing the informed consent.
- 2. Participant must have body weight of a minimum of 50.0 kg at the Screening Visit and body mass index within the range 18.0 to 32.0 kg/m² (inclusive).
- 3. Participant must be male and who is healthy as determined by medical evaluation.
- 4. Participant agrees to follow contraception guidelines in Section 10.3 (Appendix 3).
- 5. Participant must be continuous non-smoker who has not used nicotine- and tobacco-containing products for at least 3 months prior to dosing based on participant self-reporting.
- 6. Participant must be capable of giving signed informed consent as described in Section 10.1.3 (Appendix 1) which includes compliance with the requirements and restrictions listed in the ICF and in this protocol.

5.2 Exclusion Criteria

Participants are excluded from the study if any of the following criteria apply:

- 1. Have an ongoing medical history of clinically significant neurological, cardiovascular, renal, hepatic, chronic respiratory or gastrointestinal disease, psychiatric or other disorder as judged by an Investigator that could potentially affect the study outcomes or compromise participant safety.
- 2. Have clinically significant abnormal biochemistry, haematology or urinalysis results as judged by an Investigator.
- 3. Have a history of narcolepsy or sleep apnea.
- 4. Have disorders that may interfere with drug absorption, distribution, metabolism and excretion processes.
- 5. Current active hepatic or biliary disease.
- 6. Participants with cholecystectomy <90 days prior to the Screening Visit.
- 7. Positive test results for HIV-1/HIV-2 antibodies, HBsAg or Hepatitis C antibodies at the Screening Visit.
- Have a blood pressure reading outside of the following range: Systolic <86 or
 >149 mmHg; Diastolic <50 or >94 mmHg at the Screening Visit.
- Serious cardiac illness or other medical condition including, but not limited to: Uncontrolled arrhythmias

Indivior 15 May 2023

History of congestive heart failure QTcF >450 msec or history of prolonged QT syndrome Myocardial infarction Uncontrolled symptomatic angina

- 10. History of suicidal ideation within 30 days prior to providing written informed consent as evidenced by answering "yes' to questions 4 or 5 on the suicidal ideation portion of the C-SSRS completed at the Screening Visit or history of a suicide attempt (per the C-SSRS) in the 6 months prior to informed consent.
- 11. Healthy participants who are taking, or have taken, any prescribed or over-the-counter drugs (other than 2 grams of acetaminophen per 24-hour period as of Day 1 or thyroid hormone replacement therapy [see Section 6.9]) or herbal remedies in the 14 days or 5 half-lives (whichever is longer) prior to dosing of study drug.
- 12. Treatment with any known drugs that are moderate or strong inhibitors/inducers of CYP3A4 or CYP2C19, including St. John's Wort, within 30 days prior to dosing of study drug.
- 13. Any consumption of food or drink containing poppy seeds, grapefruit or Seville oranges within 14 days prior to dosing of study drug.
- 14. Regular alcohol consumption >21 units per week (1 unit = ½ pint beer, 25 mL of 40% spirit or a 125 mL glass of wine).
- 15. Positive test result for alcohol and/or drugs of abuse at the Screening Visit or at check-in.
- 16. Concurrent treatment or treatment with an investigational drug or device within 30 days or 5 half-lives (whichever is longer) prior to dosing of study drug.
- 17. Blood donation of approximately 500 mL or more within 56 days or plasma donation within 7 days prior to the Screening Visit.
- 18. Known hypersensitivity to INDV-2000.
- 19. Has less than 1 bowel movement every 2 days.
- 20. Recent history of abnormal bowel movements, such as diarrhea, loose stools or constipation, within 2 weeks prior to dosing of study drug.
- 21. Has received radiolabelled substances or has been exposed to radiation sources over the past 12 months or is likely to receive radiation exposure or radioisotopes within the next 12 months such that participation in this study would increase their total exposure beyond the recommended levels considered safe (ie, weighted annual limit recommended by the FDA 21CFR361 of 3000 mrem; FDA 2023).
- 22. Site staff and/or participants who have a financial interest in, or an immediate family member of either the site staff and/or Indivior employees, directly involved in the study.

- 23. Major surgical procedure (as defined by the Investigator) within 90 days prior to dosing of study drug or still recovering from prior surgery.
- 24. Concurrent enrolment in another clinical study, unless it is an observational study.
- 25. Participants who are unable, in the opinion of the Investigator, to comply fully with the study requirements.
- 26. Any condition that, in the opinion of the Investigator or Indivior, would interfere with evaluation of the study drug or interpretation of participant safety or study results.

5.3 Lifestyle Considerations

5.3.1 Meals and Dietary Restrictions

- 1. No water (except water provided with dosing) is allowed from 1 hour prior to and until 1 hour after dosing of study drug, but will be allowed ad libitum at all other times.
- 2. On Day 1, participants will fast overnight for at least 10 hours before and at least 4 hours after dosing of study drug.
- 3. On all days that participants are confined in the study site, meals and/or snacks will be provided at appropriate times. Each meal and/or snack served at the study site will be standardised and will be similar in caloric content and composition. Participants will not be required to fully consume any meal or snack.
- 4. Refrain from consumption of food or drink containing poppy seeds, grapefruit or Seville oranges from 14 days before dosing of study drug until after collection of the final PK sample.
- Participants should be instructed to fast for at least 12 hours before collection of fasting clinical laboratory assessment samples as indicated in Section 10.2 (Appendix 2).

5.3.2 Caffeine, Alcohol, and Tobacco

1. Participants will be instructed to abstain from ingesting caffeine- or xanthinecontaining products (eg, coffee, tea, cola drinks, chocolate) for 24 hours prior to dosing of study drug until after collection of the final PK sample.

Small amounts of caffeine derived from normal foodstuffs (eg, 250 mL/8 oz/1 cup decaffeinated coffee or other decaffeinated beverage, per day, with the exception of espresso; 45 g/1.5 oz chocolate bar per day) would not be considered a deviation to this restriction.

- 2. Participants will be instructed to abstain from alcohol for 48 hours prior to dosing of study drug until after collection of the final PK sample.
- 3. Participant will abstain from use of nicotine- or tobacco-products from 3 months before dosing of study drug and through confinement.

